10.1.2. Part 1 Expansion

Sample size in Part 1 expansion is based on clinical feasibility and consideration. No hypothesis test is planned for efficacy. Up to 35 participants will be enrolled into each treatment group. The toxicity of itacitinib will be monitored continuously for Treatment Group B and C using a Bayesian approach. A total of up to 140 participants will be enrolled into Part 1 expansion of the study. Regarding the key secondary endpoint, Month 6 response rate, a table of Bayesian posterior probabilities and related descriptions are provided below. This posterior probability may be used to support decision-making on itacitinib dosing/schedule for Part 2, including decisions made by the DMC.

Table 23 presents Bayesian posterior probability of demonstrating a clinically meaningful treatment difference in Month 6 response rate between any itacitinib group and the corticosteroids-only group under various response rates at the end of the expansion.

Table 23: Bayesian Posterior Probability to Demonstrate That There is a Clinically Meaningful Difference Between Any Itacitinib Group and the Corticosteroids-Only Group

Responders in an Itacitinib Group	Responders in Corticosteroids-Only Group (out of 35)				
(out of 35)	18	19	20	21	22
25	64.3%	54.8%	45.0%	35.3%	26.4%
26	73.1%	64.4%	54.9%	44.8%	35.0%
27	80.9%	73.4%	64.7%	54.9%	44.7%
28	87.2%	81.3%	73.9%	65.0%	55.0%
29	92.1%	87.7%	81.9%	74.4%	65.3%
30	95.5%	92.6%	88.4%	82.6%	75.0%

Note: With a binomial likelihood, binomial (n, p) with s number of responders out of n participants, and a beta prior, Beta (a, b), the posterior is calculated as Beta(a+s, b+n-s)

Interpretation:

10.1.3. Part 2

10.2. Populations for Analysis

The populations that will be included in study-related analyses are described in Table 24.

Table 24: Populations for Analysis

Population	Description			
ITT	All randomized participants.			
Safety	The safety population includes all enrolled/randomized participants who received at least 1 dose of study drug and/or reference therapy. Treatment groups for this population will be determined according to the actual treatment the participant received regardless of assigned study drug treatment.			
Safety run-in	All participants enrolled in the safety run-in portion of the study taking at least 1 dose of study drug and/or reference therapy comprise the safety run-in population. Treatment groups for this population will be determined according to the treatment assignment on Day 1 regardless of the actual study drug the participant might take during his/her continued participation in the study.			
PK evaluable	The PK evaluable population will include all participants who received at least 1 dose of study drug and/or reference therapy and provided at least 1 corresponding postdose plasma sample (1 PK measurement).			

10.3. Level of Significance

No formal statistical tests will be performed in Part 1 and Part 1 expansion. The 1-sided significance level for the analysis of the primary endpoint in Part 2 is 0.025. The 2-sided significance level for the analysis of the secondary endpoints in Part 2 is 0.05. All CIs will be 95%.

10.4. Statistical Analyses

The Statistical Analysis Plan will be developed and finalized before database lock and will describe the participant populations to be included in the analyses and procedures for accounting for missing, unused, and spurious data. This section is a summary of the planned statistical analyses of the primary and secondary endpoints.

10.4.1. Primary Analysis

10.4.1.1. Part 1 and Safety Run-In for Part 1 Expansion

The toxicity of itacitinib will be monitored continuously for each treatment group using the Bayesian approach of Thall et al (1995, 1996) as extended by Thall and Sung (1998). Dose-limiting toxicities are defined in Section 6.1.1.3.

Historical data on similar patients show a toxicity rate of 25%. The probability of toxicity for the historical data is modeled by beta distribution (Beta [25, 75]). The prior probability of toxicity for the experimental regimen is also modeled by beta distributions (Beta [0.5, 1.5]), which have the same means as the corresponding beta distributions for the historical data. Denoting the historical probability of toxicity rate by p(TOX,H), the following decision criteria will be applied:

Stop if Prob
$$\{p(TOX,H) + \delta TOX < p(TOX,E) | data \} > 0.95$$
, where $\delta TOX = 0$

Participants from each treatment group will be monitored according to the following nonbinding stopping boundaries for toxicity in Table 25. If a boundary is reached, the sponsor and external DMC will investigate and decide on the most appropriate action.

Table 25: Toxicity Stopping Boundaries

# Participants (Inclusive)	Number of DLTs Required to Stop (Inclusive)
1-2	No limit
3-4	3
5-6	4
7-9	5
10-11	6
12-14	7
15-17	8
18-19	9
20	9

10.4.1.2. Part 2

The primary endpoint is Month 6 response rate, defined as the proportion of participants demonstrating a CR or PR at Month 6 as per standard criteria (Lee et al 2015). The comparison of Month 6 response rate between treatment cohorts will be conducted once the last participant completes the Month 6 visit or withdraws from the study. A CMH test with normal approximation will be used. Summary statistics and 95% CI will be provided.

Participants who have missing data for the Month 6 response rate assessment will be considered as nonresponders.

For the interim analysis, the statistical assumptions are specified in Section 10.5.

10.4.2. Secondary Analysis

10.4.2.1. Part 1

The following secondary endpoints will be summarized by treatment group using the ITT population:

- Response rate at 3, 6, and 12 months, defined as the proportion of participants who achieved response (CR or PR) at each timepoint.
- Time to response, defined as the interval between randomization and first response.
- DoR, defined as the interval between first response and cGVHD progression, death, or initiation of new systemic cGVHD therapy.
- OS, defined as the interval between the date of randomization and the date of death due to any cause.
- NRM, defined as the proportion of participants who died due to causes other than a relapse of their primary hematologic disease.
- Proportion of participants with ≥ 50% reduction in daily corticosteroid dose at Day 180.
- Proportion of participants successfully tapered off all corticosteroids at Day 180.
- Relapse rate of malignant and nonmalignant hematologic diseases, defined as the proportion of participants whose underlying disease relapses.
- Time to primary hematologic disease relapse, defined as the interval between the date of randomization and the date of relapse. Data from clinical safety assessments (eg, AEs, infections) will be listed and tabulated by treatment group.

10.4.2.2. Part 1 Expansion

For Part 1 Expansion, the key secondary endpoints are response rate at Month 3 and Month 6, which are defined as the proportion of participants who demonstrate a CR or PR at each timepoint. The analysis will be conducted once the last participant completes Month 3 and Month 6 visits or withdraws from the study by treatment group for response rates at Month 3 and

Month 6, respectively. Summary statistics and 95% CI will be provided by cohort. The primary comparisons in Part 1 expansion will involve only the 2 itacitinib groups (A and B) and the corticosteroid alone group (D) as a result of Protocol Amendment 8, which discontinued Group C (300 mg BID + corticosteroid). Group C data will be presented only as summary statistics but will not be subjected to any statistical comparison.

Pairwise CMH tests will be conducted to Month 6 response rate for each of the 2 itacitinib groups (Treatment Group A and B) and the corticosteroids-only group (Treatment Group D) as an exploratory analysis.

The following secondary endpoints will be summarized by Treatment Groups A, B, and D using the ITT population for efficacy-related endpoints and all groups for safety-related endpoints:

- Response rate at 12 months, defined as the proportion of participants who achieved response (CR or PR) at Month 12.
- Time to response, defined as the interval between randomization and first response.
- DoR, defined as the interval between first response and cGVHD progression, death, or initiation of new systemic cGVHD therapy.
- OS, defined as the interval between the date of randomization and the date of death due to any cause.
- NRM, defined as the proportion of participants who died due to causes other than a relapse of their primary hematologic disease.
- Proportion of participants with ≥ 50% reduction in daily corticosteroid dose at Day 180.
- Proportion of participants successfully tapered off all corticosteroids at Day 180.
- Relapse rate of malignant and nonmalignant hematologic diseases, defined as the proportion of participants whose underlying disease relapses.
- Time to primary hematologic disease relapse, defined as the interval between the date of randomization and the date of relapse. Data from clinical safety assessments (eg, AEs, infections) will be listed and tabulated by treatment group.

10.4.2.3. Part 2

The following secondary endpoints will be summarized by treatment group using the ITT population:

- Parameters collected using the LSS, QOL-SF-36 v2, EQ-5D-3L, PGIC, and PGIS will be summarized. Treatment comparison will be assessed.
- Response rate at 3 and 12 months, defined as the proportion of participants who achieved response (CR or PR) at each timepoint.
- DoR, defined as the interval between first response and cGVHD progression, death, or initiation of new systemic cGVHD therapy. The comparison between treatment groups will be conducted using the log-rank test. The Kaplan-Meier method will be used. Summary statistics will be provided.

- OS, defined as the interval between the date of randomization and the date of death due to any cause. The comparison between treatment groups will be conducted using the log-rank test. The Kaplan-Meier method will be used. Summary statistics as well as overall survival for risk status will be provided.
- NRM, defined as the proportion of participants who died due to causes other than a
 relapse of their primary hematologic disease. The comparison between treatment
 groups will be conducted using a 2-sample proportion test with normal
 approximation. Cumulative incidence rates will be provided. Summary statistics and
 applicable 95% CI will be provided.
- Proportion of participants with ≥ 50% reduction in daily corticosteroid dose at Day 180. The comparison between treatment groups will be conducted using a 2-sample proportion test with normal approximation.
- Proportion of participants successfully tapered off all corticosteroids at Day 180. The comparison between treatment groups will be conducted using a 2-sample proportion test with normal approximation.
- Relapse rate of malignant and nonmalignant hematologic diseases, defined as the proportion of participants whose underlying disease relapses. The comparison between treatment groups will be conducted using the log-rank test. The Kaplan-Meier method will be used. Summary statistics will be provided.
- Time to primary hematologic disease relapse, defined as the interval between the date of randomization and the date of relapse.

Exploratory subgroup analyses and/or sensitivity analyses based on baseline prognostic factors (eg, primary hematologic disease, prior acute GVHD, type of allogeneic transplant, prior JAK inhibitors use) will be prospectively defined as part of the analyses plan and performed based on data availability.

Data from clinical safety assessments (eg, AEs, infections) will be listed and tabulated by treatment group.

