	In Part 2, approximately 246 participants will be randomized 1:1 to 1 of 2 treatment groups (123 participants per group).
Study Design	Part 1 and Part 1 expansion: randomized, open-label Part 2: randomized, double-blind, placebo-controlled
Estimated Duration of Study Participation	 It is estimated that an individual participant may participate for as long as 38 months, which includes the following: up to 28 days for screening. continuous treatment until treatment withdrawal criteria are met or for a maximum of 36 months. a minimum of 30 days for safety follow-up. post-treatment cGVHD follow-up for participants who completed itacitinib/placebo taper after initial response (CR or PR) or discontinued early for reasons other than cGVHD progression and with no requirement for new systemic cGVHD therapy (for a maximum of 24 months from Day 1). participants will be followed for survival until the participant dies or withdraws consent.

Treatment Groups and Duration:

Part 1 is a run-in that will employ a randomized, open-label, parallel-cohort design to assess the safety and tolerability of itacitinib in combination with corticosteroids (Figure 1). A total of 20 participants with moderate or severe cGVHD will be randomized 1:1 to itacitinib 200 mg QD plus corticosteroids or 300 mg QD plus corticosteroids.

[figure not shown]
Part 1 expansion is a Phase 2 with an initial safety run-in that will employ a randomized, open-label, parallel-cohort design to assess the safety and preliminary efficacy of itacitinib in combination with corticosteroids compared with corticosteroids monotherapy and select the appropriate dosing/schedule of itacitinib for Part 2 (Figure 2). A total of 140 participants (including those from Part 1) with moderate or severe cGVHD will be randomized 1:1 to 1 of 4 treatment groups that are itacitinib 300 mg QD plus corticosteroids (Treatment Group A), itacitinib 400 mg QD plus corticosteroids (Treatment Group B), itacitinib 300 mg BID plus corticosteroids (Treatment Group C) or corticosteroids monotherapy (Treatment Group D). Treatment Group C was discontinued as of Amendment 8. Randomization will be stratified by

cGVHD risk status (moderate vs severe). Treatment Groups B and C will have an initial safety run-in of 10 participants each to determine safety and tolerability of the dose before expanding.

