1. INTRODUCTION

This is a 2-part, Phase 2/3 study of itacitinib or placebo in combination with corticosteroids as initial treatment for cGVHD. Part 1 is a run-in that will employ a randomized, open-label, parallel-cohort design with the primary objective to assess the safety and tolerability of itacitinib in combination with corticosteroids in order to identify the appropriate dose of itacitinib in combination with corticosteroids as initial treatment for moderate or severe cGVHD. A total of 20 participants with moderate or severe cGVHD will be randomized 1:1 to itacitinib 200 mg QD plus corticosteroids or 300 mg QD plus corticosteroids.

Part 1 expansion is a Phase 2 with an initial safety run-in that will employ a randomized, open-label, parallel-cohort design with the primary objective to assess the safety and preliminary efficacy of itacitinib in combination with corticosteroids compared with corticosteroids monotherapy and identify the appropriate dosing/schedule of itacitinib in combination with corticosteroids as initial treatment for cGVHD for Part 2. A total of up to 140 participants (35 per treatment group) with moderate or severe cGVHD will be randomized 1:1 to 1 of 4 treatment groups: itacitinib 300 mg QD plus corticosteroids (Treatment Group A), itacitinib 400 mg QD plus corticosteroids (Treatment Group B), itacitinib 300 mg BID plus corticosteroids (Treatment Group C), or corticosteroids monotherapy (Treatment Group D). Randomization will be stratified by cGVHD risk status (moderate vs severe). Treatment Groups B and C will have an initial safety run-in of 10 participants to determine safety and tolerability of the dose before expansion. Participants enrolled in the safety run-in will be monitored continuously. Treatment Group C was discontinued as of Amendment 8, and participants in that treatment group who were ongoing were allowed to reduce to 400 mg QD plus corticosteroids.

The purpose of the original version of the SAP was to provide details of the statistical analyses that have been outlined in Part 1 of the Protocol.

The purpose of Amendment 1 is to provide details of the statistical analyses that have been outlined in Part 1 expansion of Protocol Amendment 8.

1.1. Preliminary Results From Part 1

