7.3.3. Duration of Response

Duration of response is defined as the interval between the date of initial documentation of response (CR or PR) and the date of cGVHD progression per NIH response criteria, initiation of new systemic cGVHD therapy, or death. Participants experiencing relapse of underlying hematologic relapse will be censored at the date of relapse.

Duration of response will be summarized for participants who achieve a response. Duration of response will be assessed using the Kaplan-Meier method for participants who achieve a response. Median duration and a 95% CI will be estimated. Participants who are still responding at the time of database lock or discontinuation will be right-censored at the time of last valid response assessment.

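### Part 2 plans a between-arm log-rank test on duration of response that can in effect include only responders, so its p-value is not a randomized comparison if the drug changes who responds

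*Protocol*

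**What the plan says.** Protocol 10.4.2.3 (Part 2) introduces its list with "The following secondary endpoints will be summarized by treatment group using the ITT population". The duration-of-response bullet reads "DoR, defined as the interval between first response and cGVHD progression, death, or initiation of new systemic cGVHD therapy", followed by "The comparison between treatment groups will be conducted using the log-rank test" and a Kaplan-Meier display. Protocol 10.3 adds: "The 2-sided significance level for the analysis of the secondary endpoints in Part 2 is 0.05". This is therefore a planned significance test between arms, and it can be significant in either direction.

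SAP 7.3.3 treats the same endpoint in the earlier parts of the study: "Duration of response will be assessed using the Kaplan-Meier method for participants who achieve a response". There it is only summarized. The SAP amendment states its purpose as "to provide details of the statistical analyses that have been outlined in Part 1 expansion of Protocol Amendment 8", so it does not govern Part 2. Protocol 10.4 leaves the detail of analysis populations to a SAP to be finalized before database lock.

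**The concern.** A participant who never responds has no first-response date and so no duration. The ITT label and the endpoint definition do not fit together, and nothing in Protocol 10.4.2.3 reconciles them.

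Response is also what the trial expects treatment to change: Month 6 response rate is the primary endpoint. If more people respond on itacitinib, its responders are a mixture of those who would have responded on placebo and those who respond only on drug. The placebo responders contain only the first kind. Randomization no longer protects a comparison of the two sets, and a difference may reflect who is in each set rather than how long any person's response lasts.

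At stake is a secondary-endpoint p-value that could be read as an effect on durability when it is not one. Protocol 2.3.1 says Month 6 response was chosen with durability in mind, so readers are likely to look at duration of response alongside it.

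**Working it through.** **No figure to reproduce.** The documents give no event count, hazard ratio or power for duration of response, and the text of Protocol 10.1.3 is not visible. The check asks how the planned test behaves when the drug shortens no one's response and only adds responders.

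**Inputs from the documents.** 123 per arm (Protocol Section 1, Table 3); log-rank test (10.4.2.3); 2-sided 0.05, so |z| > 1.96 (10.3).

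**Assumed inputs.** 50% respond on either arm; itacitinib adds 20 points (70%) or 10 points (60%). Durations are exponential, with a median of 24 months for those who would respond on either arm. Censoring is uniform over 3-33 months. The added responders' median is varied.

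**Hand calculation.** At the start of response, the hazard among itacitinib responders relative to placebo responders is

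w + (1 − w) × (24 / added median),

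where w is the share of itacitinib responders who would have responded anyway. With 50% vs 70%, w = 50/70 = 0.714.

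- Added median 24: 0.714 + 0.286 × 1 = 1.00
- Added median 8: 0.714 + 0.286 × 3 = 1.57
- Added median 5: 0.714 + 0.286 × 4.8 = 2.09
- 10 points added (w = 50/60 = 0.833), median 8: 0.833 + 0.167 × 3 = 1.33

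The ratio falls over time as the shorter responses end, but it starts above 1 although no individual's response was shortened. Expected responders are 0.50 × 123 = 61.5 and 0.70 × 123 = 86.1.

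**Simulation of the responder-only log-rank** (2,000 to 4,000 trials per scenario where the count is recorded; ranges are across repeat runs):

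| Added responders | Their median | Significantly against itacitinib |
|---|---|---|
| 20 points | 24 months | 2.2-2.9% (nominal 2.5%) |
| 20 points | 16 months | 7% |
| 20 points | 8 months | about 25% |
| 20 points | 5 months | 42-44% |
| 10 points | 8 months | 10-12% |
| 20 points | 36 months | 0.9% (5.7% significantly in favour) |

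**Second set of assumptions.** Response rates were taken from cells of Protocol Table 23 (20/35 = 57.1% vs 27/35 = 77.1%), with a common median of 18 months and follow-up from 6 to 18 or from 6 to 36 months. The share significantly against itacitinib was 2.1% / 2.1% when added responders had a median of 18 months, 10.5% / 13.2% at 9 months, 22.2% / 24.8% at 6 months and 50.1% / 45.8% at 3 months. In the same trials the response rate was significantly better on itacitinib about 91-93% of the time.

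**The case against.** **Responders-only is inferred.** The Part 2 text says ITT, and the SAP sentence restricting the analysis to responders belongs to the earlier parts. This stands as a matter of wording: a reader might infer that the documents state a responder-only test for Part 2, and they do not. But no other analysis is possible under the definition as written, so the restriction follows in effect.

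**The bias is conditional.** A reader might infer that the better the drug works, the more this test counts against it. The documents do not support that. It requires the added responders to have shorter responses, and no duration data are given. With equal durations the test keeps its nominal rate; with longer ones the error runs the other way. If the drug also lengthened the other responses to a median of 36 months, with added responders at 8 months, only 4.4% of trials were significantly against it. This objection stands and limits the claim to a test that can mislead in either direction.

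**Other durability evidence exists.** Month 6 response counts missing assessments as non-response, and Month 12 response is a Part 2 secondary endpoint under the same ITT lead-in. This also stands: it would be wrong to say that Part 2 has no evidence on durability in all randomized participants.

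**The consequences are limited.** The superiority claim in Protocol 10.5 rests on the primary test, and no text ties a decision to this p-value. That is true, and it bears on the weight of the point, not on whether the test is sound.

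**Conclusion.** The point holds in a conditional form. Part 2 attaches a 2-sided 0.05 log-rank test to an endpoint that exists only for responders, under an ITT label that cannot apply to it. If treatment changes who responds, the p-value is not a randomized comparison, whatever the durations turn out to be.

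Its size cannot be settled from the documents. Under the first set of assumptions above, the share of trials significantly against itacitinib runs from about 2% (equal durations) through about 25% (added median 8 months) to about 43% (5 months), and is about 10-12% with only 10 points added at 8 months. These figures show what the test can do. They do not predict that itacitinib will test worse, and the primary analysis of Month 6 response is not affected.

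**What to change.** In Protocol 10.4.2.3, and in the analysis plan for Part 2:

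1. Report duration of response among responders descriptively, with a Kaplan-Meier curve, median and 95% CI for each arm.
2. Delete the between-arm log-rank p-value for this endpoint.
3. Replace the ITT label for this endpoint with responders.

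This is a wording change and needs no new data or participants.

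If a between-arm durability comparison is wanted, define it as a separately named endpoint in all randomized participants: for example, time in response with non-responders at zero, or failure-free survival from randomization. That is an optional addition and more than a wording change, because it answers a different question. State that it combines response rate with durability. When every itacitinib response was shortened to a median of 16 months against 24, the time-in-response version still favoured itacitinib in 19% of trials.

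The time-in-response version also needs a prespecified rule for ties, because all non-responders fail together at time zero: about (0.50 + 0.30) × 123 = 98 participants at 50% vs 70%. With added responders at a median of 8 months, it favoured itacitinib in about 23-25% of trials under the standard tie variance and about 36-38% with ties broken at random.
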